MM represents a safe strategy for treating mood and anxiety disorders and potentially aspects of attentional performance in a mTBI population. However due to this population’s post-traumatic cognitive impairments, MM is a less accessible therapeutic strategy than it otherwise would be. MUSE, through its provision of NF and gamification, has the potential to help TBI patients initiate, sustain, and maintain a meditation practice. If MUSE outperforms MM on affective or cognitive outcome measurements, this study could function as a pilot study, informing future investigations of the product. If MUSE ultimately holds up in more rigorous studies, it should be recommended as a therapeutic tool to mTBI patients. If on the other hand, MUSE does not show any benefits over a regular practice of MM, the device would not be considered cost-effective and should therefore not be recommended to mTBI patients.

Specific Aims:

Aim 1: Evaluate within group differences, whether a daily, six-week practice of NF-MM or MM or a no-treatment control leads to pre- versus post-treatment changes in affective, cognitive, or mindfulness-associated variables.

Aim 2: Evaluate across-group differences, whether NF-MM outperforms MM in affective, cognitive, or mindfulness-associated variables, or whether NF-MM or MM differ from a no-treatment control group.

Aim 3: Evaluate the change in mindful attention (as measured by EEG) between NF-MM and MM groups and the no-treatment control group at the end of the intervention.

Aim 4: Evaluate the relationship between the degree of mindful attention (as measured by EEG) and affective and cognitive variables across NF-MM/MM groups as well as the no-treatment control group.

Aim 5: Evaluate acceptability of and attitudes toward NF-MM in TBI patients.

Subject Selection

Inclusion criteria: 1) history of mild-moderate TBI (per ACRM guidelines), 2) significant complaint of impaired attention or concentration, 3) ages 18-65, 4) >1 year since TBI, 5) significant cognitive function to participate in neurofeedback and mindfulness meditation, 6) has daily access to a smart phone, 7) no significant medication changes planned for the duration of the study, 8) has not had a significant meditation practice in the past.

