Treatment assignment and randomization, if applicable: Patients meeting study criteria will be randomized into one of two groups, either the NF-MM or MM group on a rolling admission. Preliminary assessment after 10 subjects enrolled in the study, demonstrated that participants in the intervention (MUSE) group had higher rates of depressive symptoms than participants in the control group. In order to balance these groups, we subsequently have decided to stratify by depression scores, such that the next five enrolled participants would be placed in the MUSE group if they had lower than average (for the study) BDI scores or the control group if they had higher than average (for the study) BDI scores. After these five subjects were enrolled, we will recalculate average BDI scores and decide whether to continue to stratify by depression scores or not.

Additionally, we have decided to add a no-treatment control group of 10 subjects. These individuals will be recruited after the first 20 subjects complete the trial. Thus, 30 subjects in total will now be part of this study.

Study Procedures

Study Site: Pre- and post-treatment assessments will be performed in outpatient offices at SRH in Charlestown or Cambridge (for those enrolled in the SRH study). MUSE training session will occur during the pre-treatment assessment session for the intervention groups. This training will last approximately 30 minutes and include a MM session with or without auditory NF.

Participants will then perform their 6 weeks of NF-MM with MUSE or MM without MUSE at their homes. Study staff will also call participants on a weekly basis, to remind patients to practice and provide technical support. A post-treatment assessment session will take place within one week of completion of the intervention. Those in the no-treatment control group, will simply undergo pre- and post-neuropsychological testing 6 weeks apart and receive meditation and MUSE training at their final 6-week visit.

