- 4) Qualitative assessment: Both NF-MM and MM groups will undergo a very brief qualitative interview at their post-treatment session to inquire on their subjective experience with MM with or without NF. The MM will then receive a MUSE device and practice NF-MM for two additional weeks, after which point they will receive a phone call with further questioning regarding their experience with MM with or without NF.

Biostatistical Analysis

First, we will power this study using the effect size that we calculate from the cognitive MUSE data collected by Bhayee et al. Then, we will compare our NF-MM, MM, and no-treatment control groups. We will contrast the three groups' cognitive outcomes in trail-making, symbol-digit coding, WAIS-IV digit spans. We will then compare affective outcomes using the Beck Anxiety Inventory, Beck Depression Inventory and Neurobehavioral Symptom Inventory. Finally we will compare mindfulness data from the Cognitive and Affective Mindfulness Scale. The continuous variables from the cognitive and affective measures will be analyzed with linear regression. The statistical contribution of demographic variables will be assessed using mixed effects models. We plan to perform post-hoc analysis for multiple comparisons.

Risks and Discomforts

Complications of procedures: We do not anticipate significant adverse effects from the use of MUSE technology, as it is already in wide use in the general population without reports of any significant harm. However, other neurofeedback studies have documented patient complaints of fatigue, feeling "spacey," anxiety, irritability, headache, or difficulty falling asleep (Hammond et al. 2011). Subjects will be able to contact study staff during daytime hours with questions or concerns regarding the possibility of such adverse effects. If these symptoms are believed to be stemming directly from use of MUSE and are intolerable for patients, they will be instructed to discontinue participation in the study.

Device complications/malfunctions: While it is not expected, it is possible for the MUSE device to malfunction. Participants will be able to email or call with tech support questions during standard business hours. Study staff members will call patients back to troubleshoot. While

equipment malfunction could interfere with data collection, it will not put patients at any risk of harm.

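### The no-treatment control is neither randomised nor concurrent, yet it is compared with both meditation groups with no stated baseline adjustment and no separate label

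*Combined protocol and SAP*

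**What the plan says.** All references are to the Combined protocol and SAP.

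- **Subject Enrollment, treatment assignment.** Chance allocation covers two groups: "Patients meeting study criteria will be randomized into one of two groups, either the NF-MM or MM group on a rolling admission". A third group of 10 was added later: "These individuals will be recruited after the first 20 subjects complete the trial". The same paragraph reports more depressive symptoms in the MUSE group after 10 enrolments. It then places the next five participants according to whether their BDI score is below or above the study average, and leaves open whether this continues.
- **Study Procedures, Study Site.** Controls have baseline data: "Those in the no-treatment control group, will simply undergo pre- and post-neuropsychological testing 6 weeks apart".
- **Specific Aims.** Aim 1 is within-group and asks whether each condition "leads to pre- versus post-treatment changes in affective, cognitive, or mindfulness-associated variables". Aim 2 is between-group and asks whether NF-MM outperforms MM, "or whether NF-MM or MM differ from a no-treatment control group".
- **Biostatistical Analysis.** "Then, we will compare our NF-MM, MM, and no-treatment control groups". On the model: "The continuous variables from the cognitive and affective measures will be analyzed with linear regression". On covariates: "The statistical contribution of demographic variables will be assessed using mixed effects models". The section does not say whether the response is the post-treatment score or the change, and it does not mention the pre-treatment score.
- **Potential Benefits.** A favourable contrast with no treatment is read, in cautious terms, as pointing to a use for meditation. The design of that contrast is not mentioned.

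**The concern.** No participant could have been allocated by chance to either meditation or no treatment, and the controls are recruited only after the first 20 have finished. The control cohort may therefore differ in referral source, severity, motivation or season. Any such difference is mixed into the meditation v no-treatment result, which is the second half of Aim 2.

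The analysis text does nothing to limit this. With response and baseline handling left open, the analyst can choose them after seeing the data. With no label, results of different evidential standing will be reported side by side.

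The baseline gap in the analysis text is not confined to the control. The same regression plan serves NF-MM v MM, where some participants were placed by BDI score.

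**Working it through.** **1. The plan's own figure.** 20 + 10 = 30, which matches the stated total. The plan gives no effect size, SD, correlation, significance level or power, so there is no power calculation to reproduce.

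**2. Which contrasts are randomised.**

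| Contrast | Allocation | Concurrent? |
|---|---|---|
| NF-MM v MM | Randomised, except five placed by BDI (5/20 = 25% of the first 20, more if the rule continues) | Yes |
| NF-MM v control | Not randomised | No |
| MM v control | Not randomised | No |

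**3. What the analysis text fixes.** It fixes linear regression for cognitive and affective measures, and mixed effects models for demographic variables. Aim 1 mentions pre-to-post change, but only within groups. Nothing states how the pre-treatment score enters a between-group contrast.

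**4. Illustration of what the open choice can do.** Every input here is an assumption: 10 v 10 (the split of the first 20 is not stated), SD 1 before and after, pre-post correlation ρ of 0.5 to 0.8, cohort shift b of 0.3, 0.5 or 0.8 SD, no true effect, two-sided 5%.

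- Unadjusted post score: noncentral t, 18 df, noncentrality = post gap × √(10×10/20) = post gap × 2.236. For a lasting gap of 0.5 this is 1.118, against a critical t of 2.101, which gives 18.5%.
- ANCOVA bias = post gap − ρ × pre gap (rejection rates by simulation, 200,000 trials per setting, 17 df).
- Change-score bias = post gap − pre gap, with SD √(2 − 2ρ), 18 df.

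Two kinds of baseline gap:

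- *Stable gap* (post gap = b): ANCOVA bias is (1 − ρ)b, change-score bias is 0.
- *Regressing gap* (post gap = ρb): ANCOVA bias is 0, change-score bias is −(1 − ρ)b. At ρ = 0.5 and b = 0.5 the change-score bias is −0.25 SD, noncentrality 0.25 × 2.236 = 0.559 in size, which gives 8.3%.

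False significance for b = 0.3 / 0.5 / 0.8 SD, range over ρ = 0.5 to 0.8:

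| Analysis | Stable gap | Regressing gap |
|---|---|---|
| Post score only | 9.7 / 18.5 / 39.5% | 6.2–8.0 / 8.3–13.5 / 13.5–27.3% |
| ANCOVA | 5.5–6.5 / 6.3–8.9 / 8.0–14.2% | about 5% |
| Change score | 5.0% | 5.5–6.2 / 6.3–8.3 / 8.4–13.5% |

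**5. Does agreement between the two methods protect?** Under either baseline-gap scenario, both are significant in the same direction in only about 3% of trials. Now suppose instead that the cohorts start level but differ by 0.3 SD in six-week change. Both methods then carry the full 0.3 SD bias:

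| ρ | ANCOVA | Change score | Both, same direction |
|---|---|---|---|
| 0.5 | 11.0% | 9.7% | 6.5% |
| 0.7 | 13.9% | 13.0% | 9.7% |
| 0.8 | 17.7% | 17.1% | 13.8% |

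Agreement is therefore no safeguard against a cohort difference in change, and a label is needed as well as an adjustment.

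**6. Cost in degrees of freedom.** In a three-group model of 30, error df are 30 − 3 = 27 (critical t 2.052), 26 with one covariate (2.056) and 25 with two (2.060).

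**The case against.** **The timing is disclosed.** This is true. The enrolment section says who is randomised and that the controls come later, and nowhere is the control called randomised. A reader might infer that the plan presents it as randomised, and the documents do not support that. What stands is that the disclosure is not carried into the analysis.

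**Baseline data exist and the cohorts share much.** This is also true. Controls are tested before and after, no separate eligibility criteria are given for them, and the outcome tests and roughly six-week interval are shared. They also receive training and a device at the end. This lowers the risk without removing it, and it means the gap lies in the analysis text, not in data collection.

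**The figures are assumed.** This is correct. The largest, 39.5%, needs both a lasting 0.8 SD gap and an unadjusted post-score analysis, and the plan does not specify that analysis. It should not be quoted as the trial's error rate.

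**ANCOVA over change scores is a preference.** On bias alone that is fair: the two are nearly mirror images, and pre-specifying either would close the choice. ANCOVA has one practical advantage. The same model serves NF-MM v MM, where its variance factor 1 − ρ² is smaller than the change score's 2 − 2ρ (0.75 v 1.00 at ρ = 0.5, 0.36 v 0.40 at ρ = 0.8).

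**The benefits paragraph is not an analysis rule and is softly worded.** Agreed. A caveat there is optional.

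**Conclusion.** The concern holds. The contrasts of NF-MM and MM with no treatment are neither randomised nor concurrent, and the plan analyses them alongside NF-MM v MM with no stated baseline adjustment and no distinction. They are open to bias from who enrols and when. The documents give nothing from which to size that bias, so the percentages above show only that the unstated choice matters and that no single choice removes the problem.

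Two stronger readings should be resisted. A reader might infer that the control comparison is worthless. The shared procedures and available baseline scores do not support that, and the comparison can stand as exploratory. A reader might also infer that NF-MM v MM is untouched. The control's timing does not affect it, but the missing baseline rule does, and the BDI-based placement means it is not fully randomised.

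This should be fixed before analysis. It is no reason to stop the study.

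**What to change.** 1. **Biostatistical Analysis, all contrasts.** State that every between-group contrast, including NF-MM v MM, is adjusted for the pre-treatment value of the same outcome (ANCOVA).
2. **Biostatistical Analysis, control contrasts.** Add a change-score sensitivity analysis. Report both results and say where they disagree. State that agreement does not rule out a cohort difference in six-week change.
3. **Treatment assignment and Biostatistical Analysis.** Label NF-MM v control and MM v control as non-randomised, non-concurrent and exploratory, and show baseline characteristics by group.
4. **NF-MM v MM.** Do not describe it as fully randomised. Say that the five participants were placed by BDI score, and include baseline BDI-II as a covariate. For the BDI-II outcome this is the covariate already in item 1.
5. **Optional.** Note in Potential Benefits that the comparison with no treatment is not randomised.

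No new data, visits or participants are needed. The cost is one error df per covariate, one or two in all, and one extra analysis per outcome. The real price is a weaker stated conclusion about meditation v no treatment.

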Potential benefits to participants: Based on the mindfulness meditation literature, participation in the NF-MM or MM arms of this study is likely to have a positive impact on a patient's mood, anxiety, and biological stress levels. It may also help with attentional impairment. Individuals in the no-treatment control group will continue with care as usual. They are not expected to benefit directly from participation in this study.

All participants in all groups will receive a Muse device in compensation for completing the study.

Potential benefits to society (e.g., increased understanding of disease processes): Information from this study could potentially be useful to mTBI patients on a population level. If NF-MM is shown to significantly outperform standard MM in terms of psychological and cognitive performance, mTBI patients and their clinicians may want to consider using MUSE following brain injury. If NF does not enhance participants' practice of MM, mTBI patients and their clinicians will want to recommend against the use of the device, as its cost does not bear out in improved outcomes. If the NF-MM or MM groups outperform the no-treatment control group, results will suggest that various types of meditation interventions may be useful for affective or cognitive symptoms in individuals with traumatic brain injury.

Monitoring and QA

Independent monitoring of source data: Study staff, physicians or psychologists, will be responsible for reviewing the accuracy and completeness of form entries, case documents, and informed consent.

Safety and outcomes monitoring: Safety and efficacy data will be reviewed on a weekly basis through email or phone correspondence between participants and either a physician or psychologist study staff member. If the practice of meditation or use of neurofeedback is causing significant psychological distress or physical discomfort, the patient will be advised to discontinue participation.

Adverse event reporting guidelines: All reports of adverse psychological and physical effects will be relayed directly to the study PI and to MUSE.

References:

<http://doi.org/10.1016/j.psychres.2013.09.002>

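### No exit interview is described for people who leave the study early, so Aim 5 is likely to overstate the acceptability of NF-MM

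*Combined protocol and SAP*

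**What the plan says.** Specific Aims sets the target: "Aim 5: Evaluate acceptability of and attitudes toward NF-MM in TBI patients".

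Data to be collected, item 4 (Qualitative assessment), gives two contacts that serve it:

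- Participants in both meditation arms, NF-MM and MM, have a "very brief qualitative interview at their post-treatment session".
- The MM group then receives a MUSE device to "practice NF-MM for two additional weeks, after which point they will receive a phone call with further questioning regarding their experience".

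Study Procedures (Study Site) fixes the timing of the first contact: "A post-treatment assessment session will take place within one week of completion of the intervention".

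Three places deal with people who do badly. Under Risks and Discomforts (Complications of procedures), if symptoms are attributed to MUSE and cannot be tolerated, "they will be instructed to discontinue participation in the study". The paragraph on psychological risk allows discontinuation when meditation brings up distressing material. Under Monitoring and QA (Safety and outcomes monitoring), if the practice or the device causes marked distress or discomfort, "the patient will be advised to discontinue participation". None of these describes an interview on leaving or any contact afterwards.

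Other information is gathered during treatment: weekly staff calls for reminders and technical help, a weekly safety and efficacy review by a physician or psychologist, and daily adherence recorded by the app in both meditation arms. None is assigned to Aim 5. The Biostatistical Analysis section has no analysis for Aim 5.

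**The concern.** For an acceptability question, leaving because of the treatment is the most informative negative answer available. Here the interview is attached to a visit that people who have left the study are not described as attending, and the protocol's own exit routes are for people who tolerate the practice or the device poorly. Who gets interviewed is thus linked to what the interview is meant to find out.

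This bears on a central argument of the study. The rationale is that feedback and gamification may help TBI patients take up meditation and keep it going, and better receptivity to the practice is one of the stated hypotheses. If the reasons for leaving are not collected, the study loses its best evidence against that argument. In an arm of about 10, each person lost is a tenth of the evidence.

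**Working it through.** **Step 1. Who can be asked about NF-MM, and when?**

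- *Assigned to NF-MM, stays in the study:* interviewed at the post-treatment session. No minimum adherence is required, so someone who has stopped practising can still attend and be heard.
- *Assigned to NF-MM, leaves the study before that session:* no acceptability contact is described.
- *Assigned to MM, stays:* interviewed at the post-treatment session, and phoned after the two weeks of NF-MM.
- *Assigned to MM, leaves:* no contact is described.

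The gap is the second group, with the fourth as its counterpart in the comparison arm. The MM phone call goes to different people and comes after the MM post-treatment session, so it cannot fill the gap.

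**Step 2. Inputs for an illustration of size.**

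The documents state no acceptability rate, dropout rate or threshold, so there is no figure to reproduce.

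- From Subject Enrollment (treatment assignment): 20 people precede the no-treatment group of 10, for a total of 20 + 10 = 30, as stated.
- Assumed: n = 10 in NF-MM, since the split of the 20 is not given.
- Assumed: 1, 2 or 3 withdrawals before the session, so d = 0.1, 0.2 or 0.3.
- Assumed: favourable share among those interviewed, pC = 80%.
- Varied: favourable share among withdrawals, pD = 0%, 50%, 80% or 100%.

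**Step 3. Formula.**

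Favourable share among all who started = (1 − d) × pC + d × pD.

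Overstatement from interviewing completers only = pC minus that share = d × (pC − pD).

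Example with 2 withdrawals, both unfavourable: 0.8 × 0.80 + 0.2 × 0 = 0.64. The overstatement is 0.80 − 0.64 = 0.16, or 16 percentage points.

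**Step 4. Results** (overstatement in percentage points, with the share among all who started in brackets; these are expected shares, not whole-person counts).

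| pD | 1 of 10 leaves | 2 of 10 leave | 3 of 10 leave |
|---|---|---|---|
| 0% | 8 (72%) | 16 (64%) | 24 (56%) |
| 50% | 3 (77%) | 6 (74%) | 9 (71%) |
| 80% | 0 (80%) | 0 (80%) | 0 (80%) |
| 100% | −2 (82%) | −4 (84%) | −6 (86%) |

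With no withdrawals the overstatement is 0 in every row.

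**Step 5. How likely is it that the gap matters at all?**

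The chance of at least one withdrawal among 10 is 1 − (1 − r)^10 for an assumed individual risk r:

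- r = 5%: 1 − 0.95^10 = 40%
- r = 10%: 1 − 0.90^10 = 65%
- r = 20%: 1 − 0.80^10 = 89%
- r = 30%: 1 − 0.70^10 = 97%

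**The case against.** Several stronger readings are tempting, and the documents do not support them.

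- *A reader might infer that acceptability is asked only at the post-treatment session.* It is not. The MM arm is also phoned after two weeks of NF-MM, which under an equal split could bring in about as many people again with experience of the device. That call still does not reach NF-MM withdrawals.
- *A reader might infer that anyone who gives up NF-MM goes unheard.* The timing sentence sets a date and does not restrict who is interviewed. Only intolerable symptoms, distress or discomfort are named as reasons to leave the study. Boredom, burden and technical trouble are not, and technical trouble gets support. Those who stop practising but remain can be interviewed.
- *A reader might infer that the bias can only run upward, or put it at 10 to 30 points.* That range needs every completer to be favourable and every withdrawal unfavourable: d × (100% − 0%) = 10, 20 or 30 points. People may leave for unrelated reasons, and the table in the working shows zero and negative values too.

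It is also fair to say that the weekly contacts, the relaying of adverse effects to the study lead and the app's adherence log would reveal much symptom-driven stopping and disuse. The endpoint is qualitative, with no stated rate, so percentages only illustrate. The study schematic and survey tools are listed as attachments that are not available here, so an exit question in them cannot be ruled out.

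These points narrow the concern without removing it. None of the other channels is tied to Aim 5, and none is described as asking those who leave what they thought of NF-MM.

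**Conclusion.** The point holds for people who leave the study before the post-treatment session. For those assigned to NF-MM, the protocol describes no way of learning their view of it, although it names exit routes that select for bad experiences. Because those routes are symptoms and distress, overstatement is the reasonable expectation, but it is not a demonstrated result.

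The size cannot be known from the documents. Under the stated assumptions it runs from a slight reversal (2 to 6 points) through zero to 24 points, and it vanishes if nobody leaves. The consequence is confined to Aim 5 and to claims about receptivity. The change is worth making because it is cheap and removes a foreseeable selection problem in a stated aim.

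**What to change.** Add to the Qualitative assessment item that every NF-MM and MM participant who leaves the study is asked the same brief questions by phone at the time of withdrawal, including the reason for leaving. Covering both arms keeps the comparison even.

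Add to the Biostatistical Analysis section a short descriptive plan for Aim 5: the number assigned to each meditation arm, the number interviewed, the number withdrawn with reasons, and the app adherence data for everyone assigned, set beside the interview findings. If the attached survey tools already contain an exit question, the protocol need only refer to it and add the reporting.

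The cost is a short amendment and a few minutes of phone time per withdrawal. Staff already phone participants weekly, and a phone interview is already planned for the MM arm. Some who leave will decline the call, so the number who decline should be reported too. No rule on when a participant stops needs to change.

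### The regression for NF-MM versus MM names neither its response nor a baseline term, although baseline BDI, itself an outcome, decides some assignments

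*Combined protocol and SAP*

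**What the plan says.** The whole model statement for these outcomes, in the Biostatistical Analysis section, is "The continuous variables from the cognitive and affective measures will be analyzed with linear regression". The only other model sentence is "The statistical contribution of demographic variables will be assessed using mixed effects models", which concerns demographics. Neither sentence names a response, a baseline score, a visit term or a group-by-visit term.

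Baseline values will exist. Under Study Procedures, "Pre- and post-treatment assessments will be performed in outpatient offices", and the Risks and Discomforts section has the BDI-II completed at both the pre- and post-test visits. BDI is listed among the affective outcomes and named again in the analysis section.

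The Subject Enrollment section, under treatment assignment and randomization, reports that "Preliminary assessment after 10 subjects enrolled in the study, demonstrated that participants in the intervention (MUSE) group had higher rates of depressive symptoms" than the control group. It goes on: "In order to balance these groups, we subsequently have decided to stratify by depression scores", so that "the next five enrolled participants would be placed in the MUSE group if they had lower than average (for the study) BDI scores", and in the control group if their scores were higher than average. After those five, the averages are to be recalculated and the team will "decide whether to continue to stratify by depression scores or not".

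**The concern.** Baseline BDI helps to decide which arm a subject enters, and BDI is then compared between the arms. When a measured variable drives assignment, the usual protection is to condition on it. The plan neither promises this nor rules it out.

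The choice of response has consequences here. The rule aims at balance, but it can undershoot or overshoot, so a gap in baseline BDI may remain. The two unadjusted forms carry such a gap into the NF-MM versus MM contrast with opposite signs. The BDI result therefore depends on a choice that the plan leaves open.

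For the other outcomes measured before treatment the stake is mainly precision, which matters with 20 subjects in the two-arm comparison.

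**Working it through.** **Figures in the plan.** The only design figure is the sample size: the first 20 subjects plus 10 no-treatment controls, 20 + 10 = 30. It is consistent. The plan gives no alpha, power, effect size, SD or pre-post correlation, so there is no power figure to reproduce. Assumed below: 10 per arm, two-sided alpha 0.05, 80% power, and r from 0.3 to 0.8.

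**Bias for a given gap.** Let D be the baseline BDI gap, NF-MM minus MM, in SD units. With no treatment effect, equal pre and post SDs and a linear relation, the expected post-treatment gap is rD. Hence:

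- 6-week score: rD
- change: rD - D = -(1-r)D
- adjusted for baseline BDI: rD - rD = 0

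Example with D = 0.5 and r = 0.7: 0.7 × 0.5 = +0.35 SD; -0.3 × 0.5 = -0.15 SD; 0. Lower BDI is better, so a positive D makes NF-MM look worse on the 6-week score and better on change. A negative D does the reverse.

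**How large D might be.** The assignment rule was simulated with no true effect and r = 0.7. The first 10 subjects are split 5/5 with MUSE higher on BDI, and the next five are placed by the 10-subject mean. The last five either fill both arms to 10 at random (rule stops) or follow the rule with the 15-subject mean (rule always continues). The plan does not report the size of the initial gap, so three thresholds were used. Approximate mean bias in SD:

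| Initial gap above | Rule stops: 6-week / change | Rule always continues: 6-week / change |
|---|---|---|
| 0 | -0.09 / +0.04 | -0.37 / +0.16 |
| 0.5 SD | +0.03 / -0.02 | -0.24 / +0.11 |
| 0.8 SD | +0.12 / -0.05 | -0.15 / +0.07 |

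If the rule continues only while MUSE is still higher (any initial gap above 0; 27% of runs continue), the bias is -0.16 / +0.07. The adjusted estimate is about 0 in every scenario. The table agrees with the formulas. In the first row the mean gap is -0.13 SD if the rule stops and -0.53 SD if it always continues: 0.7 × (-0.53) = -0.37 and -0.3 × (-0.53) = +0.16.

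**Type I error.** For any initial gap above 0, in the order stops / continues conditionally / always continues:

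- 6-week score: 3.0%, 2.8%, 8.2%
- change: 4.4%, 4.4%, 6.0%
- baseline-adjusted: 4.9%, 5.1%, 4.9%

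With initial gaps above 0.5 or 0.8 SD, the 8.2% falls below 5%.

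**Precision.** The variance of the contrast is (2/n) × V × c with n = 10. For the 6-week score V = 1, and for change V = 2(1-r), both with c = 1 and 18 df. For the baseline-adjusted model V = 1 - r², c = 1 + 1/16 and 17 df. The 80% detectable difference from the noncentral t distribution, in SD:

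| r | 6-week score | Change | Own-baseline adjusted |
|---|---|---|---|
| 0.3 | 1.32 | 1.57 | 1.31 |
| 0.5 | 1.32 | 1.32 | 1.19 |
| 0.7 | 1.32 | 1.03 | 0.98 |
| 0.8 | 1.32 | 0.84 | 0.82 |

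The factor c is the average for randomised arms; a marked baseline gap raises it somewhat.

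**The case against.** **The plan does hint at a response.** Aim 1 speaks of change from before to after treatment, and the analysis section mentions mixed models. But Aim 1 is a within-group aim. Aim 2, which compares the groups, asks only whether one outperforms the other. The mixed models are tied to demographics. Even if they were read as a repeated-measures analysis with a group-by-visit term, complete data would give the change-score contrast, not the baseline-adjusted one. The hint is fair to record but does not settle the model.

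**The harm may be small.** This largely stands. The rule is intended to balance, and the team will look again after five subjects. Most simulated biases are well below the 0.8 to 1.3 SD that the trial could detect, and post-score type I error is usually under 5%. The 8% figure needs the rule to continue regardless of that second look, after an initial gap that may have been trivial. The protocol also says that the study could serve as a pilot.

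**Stronger readings that a reader might infer, and why they fail.**

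- That the rule tilts the BDI contrast in a known direction. It does not: when the rule stops after five, the sign reverses once the initial gap exceeds 0.5 SD, and the documents do not report that gap.
- That baseline adjustment is excluded. The plan is silent on it.
- That the open choice doubles the false-positive rate. Reporting the most favourable of three forms does give 9.2% to 10.4% for one outcome. That holds for any plan that leaves the form open, was computed for plain randomisation, and nothing in the documents says it will be done.
- That every model must include baseline BDI. No bias has been calculated for outcomes other than BDI, so this does not follow.

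**Conclusion.** The point holds as a gap in the analysis plan with a clearly better method at hand. It does not show that the BDI result will be biased in a particular direction or by a particular amount.

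The opposite signs of rD and -(1-r)D follow from algebra for any r strictly between 0 and 1, given equal pre and post SDs and a linear relation. The size depends on two things the documents leave open: the initial BDI gap and whether the rule continues. Over the scenarios run at the assumed r = 0.7, the bias spans about -0.37 to +0.12 SD for the 6-week score and about -0.05 to +0.16 SD for change. Baseline adjustment stays near zero throughout, with type I error near 5% where that was tabulated. The near-zero figure comes from normally distributed, linearly related scores and would be less exact for skewed BDI data.

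The precision gain over the 6-week score is real at moderate or high r and negligible at r = 0.3.

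Two limits apply. The end-of-intervention EEG is outside this point because no pre-treatment value is described. The no-treatment group is neither randomised nor concurrent ("These individuals will be recruited after the first 20 subjects complete the trial"), so contrasts with it stay open to confounding even after adjustment.

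**What to change.** In the Biostatistical Analysis section, state the NF-MM versus MM model for each outcome with a pre-treatment value as: 6-week score = group + that outcome's own pre-treatment score. For BDI, that covariate is also the allocation variable, so one term deals with both problems.

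Adding baseline BDI to the models for the other outcomes is optional, as a sensitivity analysis. If it added no prediction, the detectable difference at r = 0.3 would go from 1.31 to 1.36 SD.

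Report the baseline BDI means by arm after 10, 15 and 20 subjects, and whether the rule was continued, so that a reader can judge the remaining gap. Label contrasts with the no-treatment group as adjusted but non-randomised.

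The cost is a few sentences and one degree of freedom per model. The pre-treatment tests are already planned, so no extra data are needed.
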